Investigate and report the safety at the time of submission of Periodic Safety Reports, at the time of completion of the registration (at the time of preparation of the 3rd or 4th Periodic Safety Report), and at the time of completion of the study (at the time of preparation of the 6th Periodic Safety Report). Report the number and ratio of patients with moderate renal impairment to all registered subjects at the time of completion of the registration (at the time of preparation of the 3rd or 4th Periodic Safety Report). Also, report the overall results of the study and the discussion of the results at the time of completion of the study (at the time of preparation of the 6th Periodic Safety Report).

15. OTHER ASPECTS

1) Amendment of the Protocol

Based on the new knowledge to be obtained according to the progress of this study, the need for amendment of the Protocol will be examined and the Study Protocol will be amended if necessary. Also, the need for amendment of the Protocol will be examined and will be amended as necessary even if the partial change in the Dosage and Administration or Indication is approved during the reexamination period (except the case when the reexamination period is newly designated), etc.

2) Actions to be taken if any problem or question is observed

In the cases where the onset of any serious and unknown adverse reaction is suggested, a significant increase in the frequency of adverse reactions is observed, any problem is found in the efficacy and safety of the drug compared to those prior to the approval, the onset of a different kind of adverse reaction is suggested, etc., the amendment of the package insert and implementation of a new special use-results survey or post-marketing clinical study should be considered.

1. REVISION HISTORY

Version/	Summary of Changes/Comments
Date/	Summary of Changes/Comments
Author(s)	
7.0	Status of Observation: Completed
19-Nov-2020	
PPD	5.4. Subgroup Analyses
	Use of diuretics (excluding potassium-sparing diuretics) in a relevant treatment for CHF/hypertension (present, absent) was added for subgroup analyses of patient characteristics.
	8.2.2. Patient Characteristics
	Subgroup Analyses of patient characteristics were added.
	Other editorial revisions.
6.0	Status of Observation: Completed
28-Sep-2020	5461 - 41
PPD	5.4. Subgroup Analyses
	For effectiveness analyses, additional subgroups were defined with respect to presence or absence of hepatic impairment, presence or absence of renal impairment, and estimated creatinine clearance (eCLCr).
	8.2.4.5.5. Plasma BNP and Serum NT-proBNP
	Serum NT-proBNP was added.
	A1.3 Definition of Visits for the Assessment of Plasma BNP and Serum NT-proBNP
	Serum NT-proBNP was added.
	Other editorial revisions.
5.0	Status of Observation: Completed
03-Jul-2020 PPD	5.4. Subgroup Analyses
	Changes were made for the category "unknown" in some categorizations.
	8.2.2. Patient Characteristics
	Handling of concomitant drugs was specified.

NIS Protocol A6141122 Statistical Analysis Plan

Version/	Summary of Changes/Comments
Date/	
Author(s)	
	In "Dosing Status of Selara Tablets", handling of treatment-discontinued patients with unknown date of last observed administration was specified.
	Other editorial revisions.
4.0	Status of Observation: Ongoing
30-Mar-2020	54.61
PPD	5.4. Subgroup Analyses
	Age categorization was revised.
	6.1. Safety Endpoints
	Other Investigation Items
	Definition of renal impairment-related events was revised.
	8.2.1. Patient Description
	Summarization of participating sites and patients by type of site was deleted.
	8.2.2. Patient Characteristics and Medical History
	The part "Patient Characteristics" was updated to include estimated glomerular filtration rate (eGFR).
	Description was updated to include handling of concomitant drugs.
	Scatter plotting of estimated creatinine clearance (eCLCr) vs. eGFR was added.
	8.2.3.1. Adverse Reactions
	Details of Adverse Reactions
	Major Investigation Items
	Other Investigation Items
	Summarization by SOC was removed from the summarizations with respect to seriousness, known/unknown, action taken, and outcome.
	Categorization of action taken was updated to include "others (none, dose increase)".
	Onset Time of Adverse Reaction
	Summarization of all adverse reactions was added.
	11.1. Appendix 1: Details of Data Extraction

NIS Protocol A6141122 Statistical Analysis Plan

Al.1 Definition of Visits for the Assessment of Dosing Status and Safety Endpoints A1.2 Definition of Visits for Cardiac Function Classification A1.3 Definition of Visits for the Assessment of Plasma BNP Description was updated to include handling of cases in which multiple values are reported on the same day. Other editorial revisions. 3.0 01-Feb-2019 PPD Status of Observation: Ongoing 9. LISTINGS Listing of contraindication violators was added. Other editorial revisions. 2.0 Status of Observation: Ongoing 5.4. Subgroup Analyses Reference subgroups for the calculation of risk ratios were specified. 6.1. Safety Endpoints Definition of an adverse reaction was revised so that no company judgement is used. Definitions of a serious adverse reaction and a serious adverse event (SAE) were added. 8. STATISTICAL METHODS AND ANALYSES The data to be included in analyses were revised with respect to their time. 8.1.4. Time-to-event Data Description of the determination of the observation time was revised to refer to another part. 8.2.2. Patient Characteristics and Medical History In "Patient Characteristics", categories for NYHA class were specified. In "Dosing Status of Selara Tablets", the summarization item "Daily dose [25 mg, 50 mg, 25 mg every 2 days, others]" was deleted because the dosage of the drug is	Version/	Summary of Changes/Comments				
Al.1 Definition of Visits for the Assessment of Dosing Status and Safety Endpoints Al.2 Definition of Visits for Cardiac Function Classification Al.3 Definition of Visits for the Assessment of Plasma BNP Description was updated to include handling of cases in which multiple values are reported on the same day. Other editorial revisions. 3.0 01-Feb-2019 PPD Status of Observation: Ongoing 9. LISTINGS Listing of contraindication violators was added. Other editorial revisions. Status of Observation: Ongoing 17-Oct-2018 PPD 5.4. Subgroup Analyses Reference subgroups for the calculation of risk ratios were specified. 6.1. Safety Endpoints Definition of an adverse reaction was revised so that no company judgement is used. Definitions of a serious adverse reaction and a serious adverse event (SAE) were added. 8. STATISTICAL METHODS AND ANALYSES The data to be included in analyses were revised with respect to their time. 8.1.4. Time-to-event Data Description of the determination of the observation time was revised to refer to another part. 8.2.2. Patient Characteristics and Medical History In "Patient Characteristics", categories for NYHA class were specified. In "Dosing Status of Selara Tablets", the summarization item "Daily dose [25 mg, 50 mg, 25 mg every 2 days, others]" was deleted because the dosage of the drug is	Date/	·				
A1.2 Definition of Visits for Cardiac Function Classification A1.3 Definition of Visits for the Assessment of Plasma BNP Description was updated to include handling of cases in which multiple values are reported on the same day. Other editorial revisions. Status of Observation: Ongoing 9. LISTINGS Listing of contraindication violators was added. Other editorial revisions. Status of Observation: Ongoing 17-Oct-2018 PPD 5.4. Subgroup Analyses Reference subgroups for the calculation of risk ratios were specified. 6.1. Safety Endpoints Definition of an adverse reaction was revised so that no company judgement is used. Definitions of a serious adverse reaction and a serious adverse event (SAE) were added. 8. STATISTICAL METHODS AND ANALYSES The data to be included in analyses were revised with respect to their time. 8.1.4. Time-to-event Data Description of the determination of the observation time was revised to refer to another part. 8.2.2. Patient Characteristics and Medical History In "Patient Characteristics", categories for NYHA class were specified. In "Dosing Status of Selara Tablets", the summarization item "Daily dose [25 mg, 50 mg, 25 mg every 2 days, others]" was deleted because the dosage of the drug is	Author(s)					
reported on the same day. Other editorial revisions. 3.0 01-Feb-2019 PPD 9. LISTINGS Listing of contraindication violators was added. Other editorial revisions. 2.0 17-Oct-2018 PPD 5.4. Subgroup Analyses Reference subgroups for the calculation of risk ratios were specified. 6.1. Safety Endpoints Definition of an adverse reaction was revised so that no company judgement is used. Definitions of a serious adverse reaction and a serious adverse event (SAE) were added. 8. STATISTICAL METHODS AND ANALYSES The data to be included in analyses were revised with respect to their time. 8.1.4. Time-to-event Data Description of the determination of the observation time was revised to refer to another part. 8.2.2. Patient Characteristics and Medical History In "Patient Characteristics", categories for NYHA class were specified. In "Dosing Status of Selara Tablets", the summarization item "Daily dose [25 mg, 50 mg, 25 mg every 2 days, others]" was deleted because the dosage of the drug is		A1.2 Definition of Visits for Cardiac Function Classification A1.3 Definition of Visits for the Assessment of Plasma BNP				
3.0 01-Feb-2019 PPD 9. LISTINGS Listing of contraindication violators was added. Other editorial revisions. 2.0 17-Oct-2018 PPD 5.4. Subgroup Analyses Reference subgroups for the calculation of risk ratios were specified. 6.1. Safety Endpoints Definition of an adverse reaction was revised so that no company judgement is used. Definitions of a serious adverse reaction and a serious adverse event (SAE) were added. 8. STATISTICAL METHODS AND ANALYSES The data to be included in analyses were revised with respect to their time. 8.1.4. Time-to-event Data Description of the determination of the observation time was revised to refer to another part. 8.2.2. Patient Characteristics and Medical History In "Patient Characteristics", categories for NYHA class were specified. In "Dosing Status of Selara Tablets", the summarization item "Daily dose [25 mg, 50 mg, 25 mg every 2 days, others]" was deleted because the dosage of the drug is		reported on the same day.				
9. LISTINGS Listing of contraindication violators was added. Other editorial revisions. 2.0 17-Oct-2018 PPD 5.4. Subgroup Analyses Reference subgroups for the calculation of risk ratios were specified. 6.1. Safety Endpoints Definition of an adverse reaction was revised so that no company judgement is used. Definitions of a serious adverse reaction and a serious adverse event (SAE) were added. 8. STATISTICAL METHODS AND ANALYSES The data to be included in analyses were revised with respect to their time. 8.1.4. Time-to-event Data Description of the determination of the observation time was revised to refer to another part. 8.2.2. Patient Characteristics and Medical History In "Patient Characteristics", categories for NYHA class were specified. In "Dosing Status of Selara Tablets", the summarization item "Daily dose [25 mg, 50 mg, 25 mg every 2 days, others]" was deleted because the dosage of the drug is	3.0					
2.0 17-Oct-2018 PPD 5.4. Subgroup Analyses Reference subgroups for the calculation of risk ratios were specified. 6.1. Safety Endpoints Definition of an adverse reaction was revised so that no company judgement is used. Definitions of a serious adverse reaction and a serious adverse event (SAE) were added. 8. STATISTICAL METHODS AND ANALYSES The data to be included in analyses were revised with respect to their time. 8.1.4. Time-to-event Data Description of the determination of the observation time was revised to refer to another part. 8.2.2. Patient Characteristics and Medical History In "Patient Characteristics", categories for NYHA class were specified. In "Dosing Status of Selara Tablets", the summarization item "Daily dose [25 mg, 50 mg, 25 mg every 2 days, others]" was deleted because the dosage of the drug is	01-Feb-2019	9. LISTINGS				
5.4. Subgroup Analyses Reference subgroups for the calculation of risk ratios were specified. 6.1. Safety Endpoints Definition of an adverse reaction was revised so that no company judgement is used. Definitions of a serious adverse reaction and a serious adverse event (SAE) were added. 8. STATISTICAL METHODS AND ANALYSES The data to be included in analyses were revised with respect to their time. 8.1.4. Time-to-event Data Description of the determination of the observation time was revised to refer to another part. 8.2.2. Patient Characteristics and Medical History In "Patient Characteristics", categories for NYHA class were specified. In "Dosing Status of Selara Tablets", the summarization item "Daily dose [25 mg, 50 mg, 25 mg every 2 days, others]" was deleted because the dosage of the drug is		Other editorial revisions.				
Reference subgroups for the calculation of risk ratios were specified. 6.1. Safety Endpoints Definition of an adverse reaction was revised so that no company judgement is used. Definitions of a serious adverse reaction and a serious adverse event (SAE) were added. 8. STATISTICAL METHODS AND ANALYSES The data to be included in analyses were revised with respect to their time. 8.1.4. Time-to-event Data Description of the determination of the observation time was revised to refer to another part. 8.2.2. Patient Characteristics and Medical History In "Patient Characteristics", categories for NYHA class were specified. In "Dosing Status of Selara Tablets", the summarization item "Daily dose [25 mg, 50 mg, 25 mg every 2 days, others]" was deleted because the dosage of the drug is	17-Oct-2018					
Definition of an adverse reaction was revised so that no company judgement is used. Definitions of a serious adverse reaction and a serious adverse event (SAE) were added. 8. STATISTICAL METHODS AND ANALYSES The data to be included in analyses were revised with respect to their time. 8.1.4. Time-to-event Data Description of the determination of the observation time was revised to refer to another part. 8.2.2. Patient Characteristics and Medical History In "Patient Characteristics", categories for NYHA class were specified. In "Dosing Status of Selara Tablets", the summarization item "Daily dose [25 mg, 50 mg, 25 mg every 2 days, others]" was deleted because the dosage of the drug is	PPD					
Definitions of a serious adverse reaction and a serious adverse event (SAE) were added. 8. STATISTICAL METHODS AND ANALYSES The data to be included in analyses were revised with respect to their time. 8.1.4. Time-to-event Data Description of the determination of the observation time was revised to refer to another part. 8.2.2. Patient Characteristics and Medical History In "Patient Characteristics", categories for NYHA class were specified. In "Dosing Status of Selara Tablets", the summarization item "Daily dose [25 mg, 50 mg, 25 mg every 2 days, others]" was deleted because the dosage of the drug is		6.1. Safety Endpoints				
The data to be included in analyses were revised with respect to their time. 8.1.4. Time-to-event Data Description of the determination of the observation time was revised to refer to another part. 8.2.2. Patient Characteristics and Medical History In "Patient Characteristics", categories for NYHA class were specified. In "Dosing Status of Selara Tablets", the summarization item "Daily dose [25 mg, 50 mg, 25 mg every 2 days, others]" was deleted because the dosage of the drug is						
8.1.4. Time-to-event Data Description of the determination of the observation time was revised to refer to another part. 8.2.2. Patient Characteristics and Medical History In "Patient Characteristics", categories for NYHA class were specified. In "Dosing Status of Selara Tablets", the summarization item "Daily dose [25 mg, 50 mg, 25 mg every 2 days, others]" was deleted because the dosage of the drug is		8. STATISTICAL METHODS AND ANALYSES				
Description of the determination of the observation time was revised to refer to another part. 8.2.2. Patient Characteristics and Medical History In "Patient Characteristics", categories for NYHA class were specified. In "Dosing Status of Selara Tablets", the summarization item "Daily dose [25 mg, 50 mg, 25 mg every 2 days, others]" was deleted because the dosage of the drug is		The data to be included in analyses were revised with respect to their time.				
part. 8.2.2. Patient Characteristics and Medical History In "Patient Characteristics", categories for NYHA class were specified. In "Dosing Status of Selara Tablets", the summarization item "Daily dose [25 mg, 50 mg, 25 mg every 2 days, others]" was deleted because the dosage of the drug is		8.1.4. Time-to-event Data				
In "Patient Characteristics", categories for NYHA class were specified. In "Dosing Status of Selara Tablets", the summarization item "Daily dose [25 mg, 50 mg, 25 mg every 2 days, others]" was deleted because the dosage of the drug is						
In "Dosing Status of Selara Tablets", the summarization item "Daily dose [25 mg, 50 mg, 25 mg every 2 days, others]" was deleted because the dosage of the drug is		8.2.2. Patient Characteristics and Medical History				
50 mg, 25 mg every 2 days, others]" was deleted because the dosage of the drug is		In "Patient Characteristics", categories for NYHA class were specified.				
adjusted as appropriate.						

•

Version/	Summary of Changes/Comments
Date/	
Author(s)	
	In "Follow-up Status", determination of the duration of follow-up for a patient was
	described for each of possible cases.
	8.2.3.4. Subgroup Analyses
	Regarding the calculation of a risk ratio for the incidence of adverse reactions, the action
	taken when the number of patients in one subgroup is small was described.
	8.2.4.1. Death
	Regarding the analysis of time-to-event data, handling of deaths with unknown date was
	described for each of possible cases.
	described for each of possible eases.
	11.1. Appendix 1: Details of Data Extraction
	A1.1 Definition of Visits for the Assessment of Dosing Status and Safety Endpoints
	A1.2 Definition of Visits for Cardiac Function Classification
	A1.3 Definition of Visits for the Assessment of Plasma BNP
	The representative date for baseline was revised from Day 0 to Day 1.
	The representative date for each time revised from Edy vite Edy 1.
	The start date of the time window for Week 1 was revised from one day after
	treatment start to the date of treatment start (after dosing).
	11.2 Appendix 2: An Example of Table Showing Risk Ratios Regarding the Incidence of
	Adverse Reaction
	An example of table was added.
	An example of table was added.
	Other editorial revisions.
1.0	Original version
29-Jun-2017	
PPD	

2. INTRODUCTION

This document describes the statistical analysis plan (SAP) of the drug use investigation of Selara® Tablets. In this SAP, citations from the corresponding study protocol are indicated in *italics*.

2.1. Study Design

This study is a multi-center cohort study of patients with chronic heart failure (CHF) receiving this drug. The investigators complete the case report form (CRF) based on source documents such as medical records that include data obtained in daily medical practice.

2.2. Objective

To confirm the safety of this drug when used in CHF patients with moderate renal impairment under actual medical practice.

3. INTERIM AND FINAL ANALYSES

In this study, interim analysis will be performed on a regular basis for the purpose of periodic safety reporting. At the time of an interim analysis, among the analyses described in this SAP only those that are required for the periodic safety reporting will be performed. At the time of the final analysis, which is performed for the purpose of re-examination application, all analyses described in this SAP will be performed.

4. HYPOTHESES AND DECISION RULES

4.1. Statistical Hypotheses

Because of the non-confirmatory nature of this study, all statistical tests in this study are considered exploratory. Unless otherwise stated, any statistical test in this study will be performed at a two-sided significance level of 5%.

4.2. Statistical Decision Rules

Not applicable.

5. ANALYSIS POPULATIONS

5.1. Safety Analysis Set

The Safety Analysis Set is the Full Analysis Set that is as close to all patients treated with Selara tablets as possible. Specifically, the Safety Analysis Set consists of all registered or reported patients except those who meet at least one of the following conditions:

a. No CRF was collected. (Indicated as "CRF not collected" in the study report.)

b. Any violation or deficiency was found concerning the study contract. (Indicated as "Contract violation/deficiency" in the study report.)

- c. The registration failed to meet all the requirements. (Indicated as "Invalid registration" in the study report.)
- d. No dosing information is reported for the study drug. (Indicated as "No dosing information" in the study report.)
- e. No information is reported for adverse events (AEs). (Indicated as "No AE information" in the study report.)

Details of each condition follow the Guidance for the Adoption/Rejection Criteria for Analysis Populations and Handling of Data in Drug Use Investigations.

5.2. Effectiveness Analysis Set

The Effectiveness Analysis Set is composed of the patients in the Safety Analysis Set excluding those who meet the following condition:

f. No effectiveness assessments are reported. (Indicated as "No effectiveness information" in the study report.)

5.3. Other Analysis Sets

Not applicable.

5.4. Subgroup Analyses

The safety of study drug will be analyzed for each of the subgroups defined according to the following patient characteristics. The underlined one in each categorization will be used as the reference when a risk ratio is calculated:

- Hepatic impairment (as assessed by the physician) (present, absent, unknown)
- Renal impairment (as assessed by the physician) (present, absent, unknown)
- Estimated creatinine clearance (eCLCr)
 (<30 mL/min, 30 mL/min <50 mL/min, ≥50 mL/min, unknown)
- Not aged (<65 years old), Aged (≥65 years old)
- Children (<15 years old), Not children (≥15 years old)
- Young-old (\geq 65, <75 years old), Old-old + oldest-old (\geq 75 years old)
- Diabetes mellitus with microalbuminuria or proteinuria (present, absent, unknown)

Safety will also be analyzed for each of the subgroups defined according to the following factors:

- Use of a relevant treatment for CHF/hypertension (present, absent) (any of the 1st to 17th drug groups, except the 2nd and 15th which are contraindicated for coadministration, listed)
- Previous treatment with device therapy (present, absent, unknown)

NYHA class (I, II, III, IV, not assessed/unknown)

As a subgroup analysis, patients who may have violated any of the contraindications indicated in the package insert of Selara Tablets ("contraindication violators", hereinafter) will be extracted according to the criteria defined separately and the safety will be assessed for this subgroup.

The effectiveness of study drug will be analyzed for each of the subgroups defined according to the following patient characteristics:

- Hepatic impairment (as assessed by the physician) (present, absent, unknown)
- Renal impairment (as assessed by the physician) (present, absent, unknown)
- Estimated creatinine clearance (eCLCr)
 (<30 mL/min, 30 mL/min <50 mL/min, ≥50 mL/min, unknown)
- Not aged (<65 years old), Aged (≥65 years old)
- Children (<15 years old), Not children (≥15 years old)
- Young-old (\geq 65, <75 years old), Old-old + oldest-old (\geq 75 years old)
- Use of a relevant treatment for CHF/hypertension (present, absent)
- NYHA class (I, II, III, IV, not assessed/unknown)
- Treatment status (completed, discontinued)

If patients included in a subgroup for safety or effectiveness analysis are limited, reviewing individual patients will be considered instead of presenting a statistical summarization.

The patient characteristics will be analyzed for each of the subgroups defined according to the following patient characteristic:

 Use of diuretics (excluding potassium-sparing diuretics) in a relevant treatment for CHF/hypertension (present, absent)

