7.3.5. Tests/clinical laboratory tests

Enter whether or not tests are implemented and test results for the clinical course from before administration of this drug to the last day of the observation period. Before administration of this drug, enter the latest test results for tests implemented during the period from three months before the start of administration to immediately before the start of administration (including the start date of administration) (For cardiac function tests: from six months before the start of administration). At the end of the observation period, enter the test results within one month after the last day of the observation period. If there are no test results for appropriate dates, enter the test results for the day of tests closest to the last day of the observation period. For any test results, enter the implementation date and test results. Regarding clinically-problematic abnormal changes in test values compared to the values before the start of administration, enter the details in the section of adverse events as well.

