7.3.5.1. Blood pressure/body weight

Blood pressure systolic, blood pressure diastolic, and body weight

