7.3.5.3. Clinical laboratory tests

Serum creatinine, serum potassium, BUN, plasma BNP, and serum NT-proBNP

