7.3.10. Major investigation items

7.3.10.1. Hyperkalaemia

Due to the mechanisms of action of this drug, a risk of hyperkalaemia is expected. It was observed as an adverse reaction in clinical studies by the time of approval. It is also known as a clinically-significant adverse reaction to similar drugs, and may become severe at the time of onset, thereby possibly threatening the life, and as such, it is specified as an important identified risk. For this event specified as a major investigation item, information on the onset date of the adverse event, procedure (change of treatment with this drug; additional treatment for the adverse event), seriousness, outcome, causal relationship with this drug, and factors for the adverse event other than this drug will be collected, and risk factors and onset time will be investigated.

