7.7. Data analyses

1) Definition of analysis sets

The safety analysis set (SAS) is defined as patients in whom treatment with this drug was confirmed.

The efficacy analysis set is defined as patients in whom treatment with this drug was confirmed and the efficacy could be evaluated in CHF patients.

2) Method of Analysis

(1) Safety analysis

Events for which a causal relationship with this drug cannot be ruled out will be handled as adverse reactions, and the number and proportion of cases of adverse reactions will be aggregated by System Organ Class and Preferred Term.

For patients with renal impairment, moderate renal impairment, or hepatic impairment, elderly patients (\geq 65 years, \geq 75 years), pediatric patients (<15 years), and diabetes patients with micro albuminuria or proteinuria, the safety will be comparatively investigated versus other populations.

In addition, the occurrence status of adverse reactions related to hyperkalaemia, renal impairment, or blood pressure decreased will be investigated in terms of risk factors and onset time.

(2) Efficacy analysis

Regarding each evaluation item for clinical evaluation, the number and proportion of cases will be aggregated by level from the results. Regarding the overall mortality and cardiovascular deaths in the study, the number of deaths and death rate (%), death rate (%) after 1 year observation period, death rate based on person-year method (the number of deaths in 100 person-year) will be calculated. For reference, the results will be compared to the domestic Phase III study or Japanese epidemiological surveys (CHART-1, CHART-2, JCARE-CARD, etc.). These comparisons will be performed with adjustment of factors such as patient background that are considered available or appropriate at the time of evaluation or setting of appropriate subgroups. ^{a)}

a. For the domestic Phase III study, comparisons to death rates adjusted for age, gender, and NYHA Functional Classification by using individual data such as patient background collected in the study will be considered; and for the Japanese epidemiological surveys, comparisons to death rates adjusted for gender and NYHA Functional Classification by using aggregate data such as patient background from published papers, etc. will be considered.

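### Baseline serum potassium and baseline blood pressure are not among the planned risk factors for hyperkalaemia and hypotension, and serum potassium has no summary table at all

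*SAP*

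**What the plan says.** For hyperkalaemia, Protocol 7.3.10.1 says that "risk factors and onset time will be investigated", and 7.3.10.2 makes the same commitment for hypotension. Protocol 7.7 repeats it as an item separate from the population comparisons: reactions of hyperkalaemia, of renal impairment and of lowered pressure "will be investigated in terms of risk factors and onset time".

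The inputs are collected. Protocol 7.3.5.1 lists "Blood pressure systolic, blood pressure diastolic, and body weight", and 7.3.5.3 lists "Serum creatinine, serum potassium, BUN, plasma BNP, and serum NT-proBNP". For the value before treatment, Protocol 7.3.5 tells sites to "enter the latest test results for tests implemented during the period from three months before the start of administration" up to and including the start date.

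SAP 5.4 opens its safety list with "The safety of study drug will be analyzed for each of the subgroups defined according to the following patient characteristics". The list covers hepatic impairment, renal impairment, eCLCr, age bands, diabetes with microalbuminuria or proteinuria, CHF/hypertension treatment, device therapy and NYHA class. There is also a group of possible contraindication violators, who "will be extracted according to the criteria defined separately and the safety will be assessed for this subgroup".

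SAP 6.1 names both blood pressure and serum potassium as safety endpoints.

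**The concern.** The level from which a patient starts is an obvious candidate when one looks for risk factors for a raised potassium or a lowered blood pressure. The protocol itself treats potassium as informative: it appears in the quoted dose-adjustment table (Table 1) and in the renal severity guide (Table 4).

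If the SAP is followed as written, no planned table shows whether hyperkalaemia clustered in patients who began with higher potassium, or hypotension-related reactions in those who began with lower pressure. The potassium distribution at the start of treatment is not shown either, overall or by renal function. A reader of the eCLCr comparison could not see whether the renal groups started from different potassium levels.

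**Working it through.** **Step 1. Follow each variable through the two documents.**

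| Place | Serum potassium | Blood pressure |
|---|---|---|
| Protocol 7.3.5, value before dosing collected | yes | yes |
| SAP 6.1, safety endpoint | yes | yes |
| SAP 5.4, safety subgroup | no | no |
| SAP 8.2.2, characteristics table | no | no |
| SAP 8.2.3.1, event-specific analyses (action taken, outcome, onset time, concomitant drugs) | no | no |
| SAP 8.2.3.3, values and changes by visit | no | yes |
| SAP 9, patient listing | yes | yes |

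SAP 6.4 (covariates) and 8.2.3.5 (exploratory safety analyses) are both marked not applicable, so nothing enters there. Appendix A1.1 includes Baseline among its visits, so 8.2.3.3 does give summary statistics for baseline blood pressure. Blood pressure is the only variable named in 8.2.3.3, so potassium has no summary at any time point.

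**Step 2. Compare the baseline windows.** Protocol 7.3.5 accepts a potassium or blood pressure value from the three months before the start. Appendix A1.1 accepts only the 30 days before the start. SAP 7 treats values outside the window as missing, without imputation. A potassium measured 60 days before the first dose would be collected and then dropped.

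**Step 3. Reproduce the plan's own figures (Protocol 7.5.2).** With rate p and n patients, the expected count is np and the 95% range is p ± 1.96 × √(p(1−p)/n).
- Hyperkalaemia, p = 0.084, n = 300: 25.2 cases, 5.26% to 11.54% (stated 5.3%-11.5%).
- Hyperkalaemia, p = 0.040, n = 1000: 40.0 cases, 2.79% to 5.21% (stated 2.8%-5.2%). The binomial 2.5% and 97.5% quantiles are 28 and 53 (stated 28-53).

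These agree, and the point disputes none of them.

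**Step 4. What could a baseline-potassium subgroup show?** The documents give neither the share of patients with higher potassium (s) nor the risk ratio (r), so both are assumptions. The overall rate is held at 4.0% with N = 1000:
- p0 = 0.04 / (1 + s(r − 1)) and p1 = r × p0
- events e1 = 1000·s·p1 and e0 = 1000·(1 − s)·p0
- SE of log r = √(1/e1 − 1/n1 + 1/e0 − 1/n0), and CI = r × exp(±1.96 × SE)
- power from the two-sided 5% normal test of two proportions

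For s = 0.10 and r = 3: p0 = 0.04/1.2 = 3.33%, p1 = 10.0%, e1 = 10, e0 = 30, SE = √(1/10 − 1/100 + 1/30 − 1/900) = 0.350, CI 1.51 to 5.95.

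| Share s | r = 2: 95% CI | Power | r = 3: 95% CI | Power |
|---|---|---|---|---|
| 5% | 0.72-5.53 | 0.32 | 1.27-7.07 | 0.65 |
| 10% | 0.92-4.35 | 0.44 | 1.51-5.95 | 0.80 |
| 25% | 1.08-3.70 | 0.59 | 1.64-5.48 | 0.92 |
| 50% | 1.05-3.81 | 0.58 | 1.48-6.07 | 0.90 |

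No such calculation is possible for hypotension, because Protocol 7.5.2 gives no rate for it.

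**The case against.** *The commitment is not broken.* The protocol promises risk factors without naming baseline potassium or pressure. SAP 5.4 covers the populations named in Protocol 7.7 and adds treatment, device therapy and NYHA class. SAP 8.2.3.1 relates concomitant drugs specifically to these events. This stands: the gap is an omission within a promised investigation, not a contradiction of the protocol.

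*Other subgroups may capture potassium.* Potassium is one of several criteria in Table 4, but SAP 5.4 uses physician-assessed renal impairment only as present, absent or unknown. The violator criteria are set out elsewhere and cannot be checked, and SAP 8.2.3.4 tabulates that group's reactions without a contrast by potassium. Neither is a substitute.

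*The listings hold the values.* True, so the information is not lost. But a listing of up to 1000 patients is not an analysis of risk factors.

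Three stronger readings are tempting and should be resisted.
- A reader might infer that baseline blood pressure is tabulated nowhere. SAP 8.2.3.3 with Appendix A1.1 tabulates it.
- A reader might infer that the primary objective fails because renal function cannot be separated from starting potassium. Protocol 6.2 asks for confirmation of safety in moderate renal impairment, not for that separation. Protocol 7.9 already discloses limited control of confounding. Because potassium is itself a Table 4 criterion, adjusting for it could also remove part of the renal effect.
- A reader might infer that potassium imbalance explains the renal contrast. The pooled counts in Protocol 7.5.2 give 22/261 (8.4%) in moderate impairment and (59 − 22)/(1471 − 261) = 37/1210 (3.1%) in the rest, a ratio of 2.76. Suppose higher potassium is present in 20% versus 5% and carries a threefold risk (assumptions). Imbalance alone then gives (1 + 0.20 × 2)/(1 + 0.05 × 2) = 1.27, and 2.76/1.27 still leaves about 2.2.

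**Conclusion.** The point holds as a gap in the risk-factor analysis and in the reporting of potassium. Neither baseline potassium nor baseline blood pressure is a safety subgroup or a listed patient characteristic. Baseline pressure is summarised by visit only, and serum potassium is not summarised at all although SAP 6.1 names it as a safety endpoint. The potassium gap is the larger of the two.

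The benefit of closing it is real but limited. On assumed shares of 10-50%, a baseline-potassium contrast has power of 0.80-0.92 for a risk ratio of 3 and 0.44-0.59 for a risk ratio of 2. If only 5% of patients fall in the higher group, these drop to 0.65 and 0.32. The figures rest on the protocol's 4.0% rate, 1000 evaluable patients and no missing baseline values; an 'unknown' group would lower them. This is an inexpensive improvement that serves a question the protocol itself asks. It does not show that the primary analysis is invalid.

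**What to change.** 1. In SAP 5.4, add baseline serum potassium and baseline systolic pressure as safety subgroups. State the categories, the reference and an 'unknown' group before the tables are run. A two-way potassium split such as <5.0 versus ≥5.0 mEq/L uses a boundary already in the protocol's tables and fits SAP 8.2.3.4, which gives risk ratios only for binary categorizations. A two-way split of systolic pressure serves the same purpose. Report hyperkalaemia reactions by baseline potassium and hypotension-related reactions by baseline systolic pressure, each with n, %, risk ratio and 95% CI.
2. In SAP 8.2.2, add baseline potassium and blood pressure, overall and by eCLCr, as is already planned for dosing status.
3. In SAP 8.2.3.3, add serum potassium to the by-visit summary.
4. State which baseline window applies to these analyses: three months (Protocol 7.3.5) or 30 days (Appendix A1.1).

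Label the additions exploratory. SAP version 7.0 itself added a diuretic subgroup after observation was complete, so a late, labelled addition matches existing practice. Leave out a table of hyperkalaemia by eCLCr within potassium strata, or keep it purely descriptive: two potassium categories plus 'unknown' crossed with four eCLCr categories make 12 cells for about 40 events, roughly 3 per cell.

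The cost is SAP wording and a few tables from data already collected. The downsides are an 'unknown' category, some small cells and low precision for moderate effects. The categories are for analysis only and imply no dosing or clinical rule.
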